## 5.1 Follow-up for Ineligible Patients

The follow-up requirements for ineligible patients who have received no protocol therapy include submission of the Baseline Report. Data submission for ineligible participants who have received at least one dose of protocol therapy should be followed according to the protocol to allow for treatment and adverse event assessment.

## 6.0 ENTRY/REGISTRATION PROCEDURES

### 6.1 Entry Procedures

All registrations will be done through the CCTG web-based, password-operated Electronic Data Capture (EDC) system. Complete details regarding obtaining a password, accessing the system and registering patients will be provided at the time of study activation and will also be included in the “EDC Data Management Guidebook”, posted on the IND.224 trial specific web-site. If sites experience difficulties accessing the system and/or registering patients please contact the help desk (link in EDC) or the IND.224 Study Coordinator.

All eligible patients enrolled on the study by the participating treatment centre will be assigned a serial number which must be used on all documentation and correspondence with CCTG.

The following information will be required:

- trial code (CCTG IND.224)
- patient's initials (may be coded)
- informed consent version date, date signed by patient, name of person conducting consent discussion and date signed
- confirmation of the requirements listed in Section 4.0, including dates of essential tests and actual laboratory values
- height and weight

### 6.2 Registration

Registration will be provided electronically.

*Note:* The validity of results of the trial depends on the authenticity of and the follow-up of all patients entered into the trial. Under no circumstances, therefore, may an allocated patient's data be withdrawn prior to final analysis, unless the participant withdraws from the trial and requests that data collection/submission cease from the point in time of withdrawal.

All eligible patients admitted to the trial will be followed by the coordinating centre. It is the responsibility of the physician in charge to satisfy himself or herself that the patient is indeed eligible before requesting registration/randomization.

All registered patients are to be followed until death or until sites are informed by CCTG that further follow-up is no longer required. The follow-up requirements for ineligible patients who have received no protocol therapy include submission of the Baseline Report. Data submission for ineligible participants who have received at least one dose of protocol therapy should be followed according to the protocol to allow for treatment and adverse event assessment.

## 7.0 TREATMENT PLAN

Although the Canadian Cancer Trials Group acts as the coordinating agency for the trial, the responsibility for treatment of patients rests with the individual investigator.

In accordance with CCTG policy, protocol treatment is to begin within 2 working days of patient registration.

Patients should begin taking dabrafenib and trametinib a minimum of 7 days and a maximum of 14 days prior to commencement of SRS.

There will be 2 cohorts of patients. Each cohort is based on the number of brain metastases at presentation on T1-post gadolinium volumetric axial MRI.

Cohort 1: minimum 20 to 25 patients

Patients with 1-4 metastases will receive focal SRS to all lesions and dabrafenib + trametinib. Agents will begin a minimum of 7 days and a maximum of 14 days prior to SRS and continue post-SRS until progression or unacceptable toxicity.

Cohort 2: minimum 20 to 25 patients

Patients with 5-10 metastases will receive focal SRS to all lesions and dabrafenib + trametinib. Agents will begin a minimum of 7 days and a maximum of 14 days prior to SRS and continue post-SRS until progression or unacceptable toxicity.

### 7.1 Chemotherapy Treatment Plan

#### 7.1.1 Drug Administration

Cohort	Agent(s)	Route	Dose	Frequency	Schedule
1 & 2	Dabrafenib	PO	150 mg	BID	Continuously*
	Trametinib	PO	2 mg	OD	

\* A treatment cycle (reporting period) is defined as 28 days. There will be no breaks between cycles.

#### 7.1.2 Premedication

Not required. Prophylactic corticosteroids are not required but may be used prior to SRS based on institutional standards and investigator discretion. The following is an example regimen:

- Prophylactic dexamethasone at 10 mg IV 1 hour prior to start of SRS.
- Prophylactic dexamethasone at 4 mg po in am per day of fractionated SRS is permitted according to institutional practice.

#### 7.1.3 Dose Modifications

*For New Primary Cutaneous Malignancies:*

No dose modifications are required.

*For New Primary Non-Cutaneous Malignancies:*

No dose modifications are required for trametinib. If used in combination with dabrafenib, permanently discontinue dabrafenib in patients who develop RAS mutation-positive non-cutaneous malignancies.

Doses will be reduced for adverse reactions as described in Table 2.

Dose Level	Dabrafenib	Trametinib
-1	100 mg orally twice daily	1.5 mg orally once daily
-2	75 mg orally twice daily	1 mg orally once daily
-3	50 mg orally twice daily	Permanently discontinue
-4	Permanently discontinue	

*Table 2: Recommended Dose Modifications for Trametinib and Dabrafenib Administered in Combination*

Severity of Adverse Reaction *	Trametinib	Dabrafenib
Febrile drug reaction		

 
• Fever of 38.5-40°C without complications
 
	
 
• Trametinib may be continued at the same dose.
 
	
 
• Withhold dabrafenib until fever resolves. Then resume at same or lower dose level.
 

 
• Fever higher than 40°C
 
• Fever complicated by rigors, hypotension, dehydration, or renal failure
 
	
 
• Withhold trametinib until fever resolves. Then resume trametinib at same or lower dose level.
 
	
 
• Withhold dabrafenib until fever resolves. Then resume at a lower dose level.
 
 
Or
 
 
• Permanently discontinue dabrafenib.
 

Cutaneous		

 
• Grade 2 rash (tolerable)
 
	
 
• Reduce dose of trametinib by 0.5 mg or discontinue in patients taking 1 mg daily
 
	
 
• Dabrafenib may be continued at the same dose. Monitor as clinically indicated.
 


 
• Intolerable Grade 2 rash or <math>\geq</math> Grade 3 rash
 
	
 
• Withhold trametinib for up to 3 weeks. If improved within 3 weeks, resume at a lower dose (reduced by 0.5 mg) or discontinue in patients taking 1 mg daily
 
	
 
• Withhold until adverse reaction resolves or improves to Grade 1 and reduce by one dose level when resuming therapy
 

 
• Intolerable Grade 2 or <math>\geq</math> Grade 3 rash that does not improve within 3 weeks despite interruption of dosing
 
	
 
• Permanently discontinue trametinib
 
	
 
• Permanently discontinue treatment with dabrafenib
 

*table continues on next page ...*

Severity of Adverse Reaction*	Trametinib	Dabrafenib
Cardiac		

 
Asymptomatic, absolute decrease in LVEF of 10% or greater from baseline and is below institutional lower limits of normal (LLN) from pre-treatment value
 
	
 
Withhold trametinib for up to 4 weeks.
 
	
 
Dabrafenib may be continued at the same dose. Monitor as clinically indicated.
 

 
Asymptomatic, absolute decrease in LVEF of 10% or greater from baseline and is below LLN that improves to normal LVEF value within 4 weeks following interruption of trametinib
 
	
 
Resume trametinib at a lower dose (reduced by 0.5 mg) or discontinue in patients taking 1 mg daily
 
	
 
Dabrafenib may be continued at the same dose. Monitor as clinically indicated.
 

 
Absolute decrease in LVEF of 10% or greater from baseline and is below LLN that does not improve to normal LVEF value within 4 weeks following interruption of trametinib
 
	
 
Permanently discontinue trametinib
 
	
 
Dabrafenib may be continued at the same dose. Monitor as clinically indicated.
 


 
Symptomatic congestive heart failure
 
Absolute decrease in LVEF of greater than 20% from baseline that is below LLN
 
	
 
Permanently discontinue trametinib
 
	
 
Withhold dabrafenib until adverse reaction resolves and resume dabrafenib at the same dose or at a reduced dose level.
 

Ocular Toxicities		

 
Grade 2-3 retinal pigment epithelial detachments (RPED)
 
	
 
Withhold trametinib for up to 3 weeks.
 
	
 
Dabrafenib may be continued at the same dose. Monitor as clinically indicated.
 

 
Grade 2-3 RPED that improves to Grade 0-1 within 3 weeks
 
	
 
If improved within 3 weeks, resume trametinib at a lower dose (reduced by 0.5 mg) or discontinue in patients taking 1 mg daily
 
	
 
Dabrafenib may be continued at the same dose. Monitor as clinically indicated.
 

 
Grade 2-3 RPED that does not improve to at least Grade 1 within 3 weeks OR recurrence of RPED (any Grade) after dose interruption or reduction
 
	
 
Permanently discontinue trametinib
 
	
 
Dabrafenib may be continued at the same dose. Monitor as clinically indicated
 

 
Retinal vein occlusion
 
	
 
Permanently discontinue trametinib.
 
	
 
Dabrafenib may be continued at the same dose. Monitor as clinically indicated.
 

 
Uveitis that responds to local ocular therapy
 
	
 
Trametinib may be continued at the same dose
 
	
 
Dabrafenib may be continued at the same dose. Monitor as clinically indicated.
 


 
Uveitis that does not improve despite ocular therapy
 
	
 
Withhold trametinib until adverse reaction resolves and resume at the same or a reduced dose
 
	
 
Withhold dabrafenib until adverse reaction resolves and reduce by one dose level when resuming therapy
 

Pulmonary		

 
Interstitial lung disease/pneumonitis
 
	
 
Permanently discontinue trametinib.
 
	
 
Dabrafenib may be continued at the same dose. Monitor as clinically indicated.
 

*table continues on next page ...*

Severity of Adverse Reaction*	Trametinib	Dabrafenib
Other		
• Grade 1 or Grade 2 (tolerable)	Trametinib may be continued at the same dose. Monitor as clinically indicated.	• Dabrafenib may be continued at the same dose. Monitor as clinically indicated.
• Grade 2 (intolerable) OR Grade 3 adverse reaction	• Withhold trametinib. If adverse reaction resolves or improves to Grade 1, reduce by one dose level when resuming therapy.	• Withhold dabrafenib until adverse reaction resolves or improves to grade 1 and reduce by one dose level when resuming therapy.
• Grade 4 adverse reaction OR Grade 3 adverse reaction that does not improve to Grade 0-1	• Permanently discontinue trametinib.	• Permanently discontinue dabrafenib OR withhold therapy until adverse reaction resolves or improves to Grade 1 and reduce by one dose level when resuming therapy.

\* Adverse events will be graded using the NCI Common Terminology Criteria for Adverse Events (CTCAE) (see Appendix V).

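### Table 2 (Cardiac): on trametinib 2 mg or 1.5 mg, an asymptomatic LVEF fall of more than 20 points to below LLN that recovers within 4 weeks meets both a resume row and a permanent-stop row, with no stated precedence

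*Combined protocol and SAP*

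**What the plan says.** The protocol's only LVEF dosing rules are the four cardiac rows of Table 2 in Section 7.1.3. The sentence introducing the table says that doses will be reduced as the table describes. The caption reads "Recommended Dose Modifications for Trametinib and Dabrafenib Administered in Combination".

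- **Row 1:** an asymptomatic absolute fall of 10% or more, to below LLN. Trametinib is withheld for up to 4 weeks.
- **Row 2:** "Asymptomatic, absolute decrease in LVEF of 10% or greater from baseline and is below LLN that improves to normal LVEF value within 4 weeks" of interrupting trametinib. Action: "Resume trametinib at a lower dose (reduced by 0.5 mg) or discontinue in patients taking 1 mg daily".
- **Row 3:** an absolute fall of 10% or more that "is below LLN that does not improve to normal LVEF value within 4 weeks following interruption of trametinib". Trametinib is stopped permanently. This row does not repeat the word asymptomatic.
- **Last row:** two bullets, symptomatic congestive heart failure and "Absolute decrease in LVEF of greater than 20% from baseline that is below LLN". Action: "Permanently discontinue trametinib".

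For dabrafenib, rows 1 to 3 say "Dabrafenib may be continued at the same dose. Monitor as clinically indicated". The last row says "Withhold dabrafenib until adverse reaction resolves and resume dabrafenib at the same dose or at a reduced dose level".

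Section 9.1 makes certain LVEF decreases reportable and refers back to Table 2. Section 10.1 lists unacceptable toxicity, as defined in Section 7.0, as a reason to stop treatment. Neither ranks the cardiac rows.

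**The concern.** Rows 1 and 2 have a floor for the size of the fall but no ceiling. The large-fall bullet in the last row has a size condition but none on symptoms or recovery. A large, silent, reversible fall therefore fits both, and the trametinib instructions for it are opposite: restart at a lower dose, or never restart.

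At stake is whether a patient is re-exposed to a drug that the same table says to stop permanently, and whether two sites would handle the same event alike. Section 9.1 does not help, because it sorts asymptomatic decreases by whether they recover, not by size. A site reading it alongside Table 2 could be steered towards row 2.

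**Working it through.** The plan gives no figure to reproduce. The check compares the triggers and then the actions.

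**Inputs.** Triggers and actions come from the cardiac rows of Table 2. Trametinib doses of 2, 1.5 and 1 mg come from Sections 7.1.1 and 7.1.3. LLN is institutional and not given, so 50% and 55% are assumed. B is baseline LVEF, V the lowest follow-up value and L the LLN. The table's percentages are absolute, so they are read as points.

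**Triggers, asymptomatic patient**
- Row 1: B − V ≥ 10 and V < L. Row 2: the same, plus return to normal within 4 weeks.
- Last row, second bullet: B − V > 20 and V < L.

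Any fall above 20 is also at least 10, so for asymptomatic patients the last row's region lies wholly inside row 1's. Adding recovery within 4 weeks puts the patient in row 2 as well.

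**Where the overlap starts (whole-number V)**

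| Assumed L | B | 10-point trigger only | Both triggers |
|---|---|---|---|
| 50 | 60 | 40–49 | ≤ 39 |
| 50 | 65 | 45–49 | ≤ 44 |
| 50 | 70 | none | ≤ 49 |
| 55 | 65 | 45–54 | ≤ 44 |
| 55 | 70 | 50–54 | ≤ 49 |
| 55 | 75 | none | ≤ 54 |

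**Worked case (assumed values).** L = 50, B = 65, V = 42, back to 56 at week 3. The fall is 65 − 42 = 23, which is at least 10 and more than 20, and 42 < 50. Both rows apply.

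**Trametinib action after recovery**

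| Current dose | Row 2 | Last row | Conflict |
|---|---|---|---|
| 2 mg | 2 − 0.5 = 1.5 mg | stop permanently | yes |
| 1.5 mg | 1.5 − 0.5 = 1 mg | stop permanently | yes |
| 1 mg | discontinue | stop permanently | no |

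Without recovery, row 3 and the last row both stop trametinib permanently. At detection, both row 1 and the last row stop dosing, one temporarily and the other for good. The opposing instructions surface on recovery.

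**How many patients.** Section 2.0 cites an LVEF decrease in 4% of patients in a phase III trial of the combination. Section 12.3 sets a maximum of 50 patients. If that rate holds here (assumption), 0.04 × 50 = 2 patients would have any LVEF decrease. The conflict needs one that is also asymptomatic, more than 20 points, below LLN, recovered within 4 weeks, and in a patient on 2 or 1.5 mg. The documents do not give that share, so under this assumption the expected number lies between 0 and 2. Detection pushes it down: after baseline, ECHO/MUGA is done only as clinically indicated (treatment schema; Section 5.0), so many silent falls would go unseen and no scheduled scan documents recovery by week 4.

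**The case against.** The strongest reply is that the table's structure already settles the matter. Its first column is headed by severity, and the large-fall row is the top cardiac tier. That row's trigger is met at detection, so a site applying it then has nothing left to resume, and row 2 presupposes the temporary interruption of row 1. The other reading leaves the large-fall bullet almost no work for trametinib: heart failure has its own bullet, row 3 handles unrecovered falls, and at 1 mg row 2 also discontinues. This is persuasive evidence of intent, and it stands. It does not supply a rule. Elsewhere Table 2 separates tiers in words: the lower fever tier is capped at 40°C and excludes complications. The lower LVEF tier has no such cap.

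Reading the two bullets of the last row as jointly required would remove the overlap. But the higher fever row uses the same format for what are naturally alternatives, and a joint reading would leave heart failure with a smaller fall outside the last row.

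The word recommended in the caption softens the table, but the introducing sentence makes it operative.

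Three stronger readings are tempting and not supported:
- *The table contradicts itself for every fall above 20 points.* It does not: LVEF must also fall below LLN and recover within 4 weeks, and the dose must be above 1 mg.
- *Dabrafenib instructions also contradict each other.* Rows 1 to 3 only permit continuation. Withholding satisfies all rows, so this is unclear wording, not a conflict.
- *The event is reasonably likely in this trial.* Assuming that 10% to 25% of LVEF decreases fall in the conflict zone would give a chance of at least one case of 1 − 0.996^50 = 0.18 to 1 − 0.99^50 = 0.39. Nothing in the documents supports that share, and it allows neither for limited detection nor for the dose condition.

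**Conclusion.** Wrong as written, and minor. For one narrowly defined patient, Table 2 gives two incompatible trametinib instructions and no order between them. The overlap follows from the wording alone, whatever LLN is assumed. That the last row is meant to govern is likely but remains an inference.

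Few or no patients are expected to be affected; the documents support nothing more precise. Most investigators would probably take the stricter row, and that choice is always open to them. The sample size and the primary analysis of intracranial response are not affected.

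**What to change.** Either change is sufficient:

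1. Cap rows 1 and 2 at an absolute fall of 10 to 20 points. An asymptomatic fall of more than 20 points to below LLN then has one trametinib outcome.
2. Add to the last cardiac row: *either criterion is sufficient, with or without symptoms; this row overrides the rows above.*

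The second is slightly better because it also makes clear that dabrafenib is withheld. That includes a patient with symptomatic heart failure and an unrecovered fall of 10 to 20 points, who meets both row 3 and the last row. A reader might infer from that case that the cap is inadequate. It is not, for this conflict: both rows stop trametinib there, and only the dabrafenib wording differs.

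The cost is one wording change in Table 2, with no added procedure, visit or patient.

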## 7.2 Concomitant Medications and Non-Drug Therapies

### 7.2.1 Permitted Medications and Non-Drug Therapies

The investigator must be informed as soon as possible about any medication taken from the time of screening until 30 days after the last dose of study treatment. Any concomitant medication(s), including dietary supplements, taken during the study will be recorded in the eCRF. The minimum requirement is that drug name, dose, and the dates of administration are to be recorded. Additionally, a complete list of all prior surgical procedures will be recorded in the eCRF.

Subjects should receive full supportive care during the study, including transfusions of blood and blood products, and treatment with antibiotics, anti-emetics, anti-diarrheals, and analgesics, and other care as deemed appropriate, and in accordance with their institutional guidelines. Use of anticoagulants such as warfarin is permitted provided that INR is monitored in accordance with local institutional practice.

### 7.2.2 Prohibited Medications and Non-Drug Therapies

The use of certain medications and illicit drugs within 28 days or 5 half lives, whichever is shorter, prior to registration and for the duration of the study will not be allowed.

The following medications or non-drug therapies are also prohibited while on treatment in this study:

- Other anti-cancer therapies;
- Other investigational drugs;
- Antiretroviral drugs (Note: Subjects with known HIV are ineligible for study participation);
- Herbal remedies (e.g. St. John's Wort);

- Dabrafenib is metabolized primarily by Cytochrome P450 (CYP) 2C8 and CYP3A4. Co-administration of dabrafenib with ketoconazole, a CYP3A4 inhibition, or with gemfibrozil, a CYP2C8 inhibitor, resulted in increases in dabrafenib AUC of 71% and 47%, respectively. Drugs that are strong inhibitors or inducers of CYP3A and CYP2C8 (see list in Table 3) may only be used under special circumstances (e.g. as a single use for a procedure) while treatment with study drug is interrupted as they may alter dabrafenib concentrations; consider therapeutic substitutions for these medications. Approval of the CCTG Senior Investigator is required in these situations. The list may be modified based on emerging data. Refer to the SPM for the most current list.

*Table 3: Prohibited Medications*

PROHIBITED	
– strong inducers of CYP3A or CYP2C8, since concentrations of dabrafenib may be decreased	
Class/Therapeutic Area	Drugs/Agents
Antibiotics	Rifamycin class agents (e.g., rifampin, rifabutin, rifapentine),
Anticonvulsant	Carbamazepine, oxcarbazepine phenobarbital, phenytoin, s-mephénytoïn
Miscellaneous	bosentan, St. John's wort
PROHIBITED	
– Strong inhibitors of CYP3A, or CYP2C8 since concentrations of dabrafenib may be increased	
Class/Therapeutic Area	Drugs/Agents
Antibiotics	Clarithromycin, telithromycin, troleandomycin
Antidepressant	Nefazodone
Antifungals	Itraconazole, ketoconazole, posaconazole, voriconazole
Hyperlipidemia	Gemfibrozil
Antiretroviral	ritonavir, saquinavir, atazanavir
Miscellaneous	Conivaptan

#### 7.2.3 Medications to be Used With Caution

The following medications should be used with caution as their concentrations may be altered by dabrafenib or they may alter dabrafenib concentrations:

- Drugs that are moderate inhibitors or inducers of CYP3A and CYP2C8 as they may alter concentrations of dabrafenib.
- Dabrafenib has been shown to induce CYP3A4 and CYP2C9 in vivo using midazolam (CYP3A4 substrate) and S-warfarin (CYP2C9 substrate). Dabrafenib is an in vitro inducer of CYP2B6 and other enzymes such as CYP2C8, CYP2C19, UDP-glucuronyl transferases. Transporters may also be affected. Co-administration of dabrafenib and medications which are affected by the induction of these enzymes (including warfarin) and transporters may result in loss of efficacy. If co-administration of these medications is necessary, investigators should monitor subjects for loss of efficacy or consider substitutions of these medications. A partial list of these medications is provided in the SPM.

- Therapeutic level dosing of warfarin can be used with close monitoring of PT/INR by the site. Exposure decreased by 37% due to enzyme induction when on treatment, thus warfarin dosing may need to be adjusted based upon PT/INR. Consequently, when discontinuing dabrafenib, warfarin exposure may be increased and thus close monitoring via PT/INR and warfarin dose adjustments must be made as clinically appropriate. Prophylactic low dose warfarin may be given to maintain central catheter patency.
- Dabrafenib solubility is pH-dependent with decreased solubility at higher pH. Drugs such as proton pump inhibitors that inhibit gastric acid secretion to elevate gastric pH may decrease the solubility of dabrafenib and reduce its bioavailability. No clinical study has been conducted to evaluate the effect of pH on dabrafenib pharmacokinetics. In an ad-hoc analysis, no differences in Cmax and AUC were noted between subjects who reported taking pH-elevating products relative to other subjects. Due to the theoretical risk that pH-elevating agents may decrease oral bioavailability and exposure to dabrafenib, these medicinal products that increase gastric pH should be used with caution when administered with dabrafenib.

